# 2. STATISTICAL HYPOTHESES

There is no hypothesis testing in this study; all analysis will be performed in a descriptive manner. Means and proportions for different objectives will be computed with their 95% confidence intervals (CIs).

## 2.1. Multiplicity Adjustment

N/A

# 3. ANALYSIS SETS

## 3.1. Definition

#### Table 5Analysis sets

Analysis set	Description	Analyses Evaluated
Screened	All participants who were screened for eligibility.	Study Population
Enrolled	Participants who completed the informed consent process,	Study Population
	meet screening/eligibility criteria and undergone an invasive	
	procedure.	
	Note: screening failures (who never passed screening even if	
	re-screened) and participants screened but never enrolled	
	into the study (Met eligibility but not needed) are excluded	
	from the Enrolled analysis set as they did not enter the study.	
Exposed	All participants who received the dose of the study	Safety excluding solicited AE
	intervention. Analysis per group using the enrolled set based	
	on the administered intervention.	
Per Protocol	All eligible participants who received dose of study	Immunogenicity
	intervention as per protocol, without intercurrent conditions	
	that may interfere with immunogenicity and without prohibited	
	concomitant medication/vaccination, and who have values for	
	pre-dose and post-dose neutralizing titer against pseudovirus	
	bearing BA. 5 S protein data for the relevant timepoint, and	
	without major protocol deviations.	
	The PPS for immunogenicity will be defined by time point.	
Solicited	All participants who received the dose of the study	Safety
Safety	intervention (Exposed Set) who have reported the presence	
	or absence of any solicited AE at least once.	

AE: Adverse event; D: Day; S: Spike; PPS: Per Protocol Set

# 4. STATISTICAL ANALYSES

## 4.1. General Considerations

Standard data derivation rules and statistical methods are described in section 6.2.

Unless otherwise specified, analysis of safety endpoints will be performed on the Exposed Set. The primary analysis of the immunogenicity endpoints will be performed on the Per Protocol Set (PPS).

## 4.1.2. Baseline Definition

For all endpoints the baseline value will be the latest pre-dose assessment with a nonmissing value, including those from unscheduled visits. If time is not collected, Day 1 assessments are assumed to be taken prior to first dose and used as baseline.

Unless otherwise stated, if baseline data is missing no derivation will be performed and baseline will be set to missing.

## 4.2. Primary Endpoint(s) Analyses

## 4.2.1. Safety and Reactogenicity

## 4.2.1.1. Analysis of safety and reactogenicity planned in the protocol

Solicited safety endpoints will be performed on the Solicited Safety Set. Unsolicited safety endpoints will be performed on the Exposed Set. Other adverse events/medically attended events, and safety lab data will be performed on the Exposed Set.

Primary Safety Endpoints	Statistical Analysis Methods
Solicited administration site events and systemic events during the 7-day follow-up period after study vaccine administration (day of study vaccine administration and 6 subsequent days);	Solicited AEs are prespecified as administration site and systemic. Solicited AEs are AEs with onset from Day 1 – Day 7 after the dosing and captured in eDiary. The number and percentage with exact 95% Cl of participants reporting at least one solicited administration site event, with at least one solicited systemic event, and with any solicited AE during the 7- day period (i.e. with onset from Day 1- Day 7 post vaccination) will be tabulated by treatment group. The same tabulations will be performed for Grade 3 AEs.
	The number and percentage with exact 95% CI of participants reporting each individual solicited administration site event (any grade, Grade 1, Grade 2, Grade 3, medically attended events) and solicited systemic event (any grade, Grade 1, Grade 2, Grade 3, medically attended events) during the 7-day follow-up period (i.e. with onset from Day 1- Day 7 post vaccination) will be tabulated by maximum intensity per participant for each treatment group.
Unsolicited AEs during the 30-day follow-up period after study vaccine administration (day of study vaccine administration and 29 subsequent days);	The number and percentage with exact 95% CI of participants reporting at least one unsolicited AE during the 30-day follow-up period (i.e. with onset from Day 1 to Day 30 post vaccination), as classified by the Medical Dictionary for Regulatory Activities (MedDRA) System Organ Class (SOC) and Preferred Term (PT) will be tabulated by treatment group.
	The same tabulations will be performed for Grade 3, any causally related, Grade 3 causally related unsolicited AEs and unsolicited AEs with medically attended visits. In the AE summaries, a participant with 2 or more AEs within the same SOC or PT level but different relationship will be counted only once in the level using the related incident.
Any hematological and biochemical laboratory abnormality during the 15-day follow-up period after study vaccine administration (day of study vaccine administration and 14 subsequent days);	
 
For each treatment group and for each Hematology and biochemistry parameter:
 
The number and percentage with exact 95% CI of participants having hematology and biochemistry results below, within, or above the laboratory normal ranges will be tabulated by time point.
 
The number and percentage of subjects reporting a grading increase from baseline at Day 8 and
 

Primary Safety Endpoints	Statistical Analysis Methods
	Day 15 separately. The maximum grading post
	vaccination up to Day 15 (i.e. Day 1 – Day 15) will
	be tabulated versus baseline. Grades will be
	based on the FDA guidance for industry "Toxicity
	grading scale for healthy adults and adolescent
	volunteers enrolled in preventive vaccine clinical
	trials" (Protocol Section 10.2.2).
	The listing of safety laboratory results will be
	provided
MAAEs; SAEs; AESIs up to D31.	The number and percentage with exact 95% CI of
	participants reporting MAAEs, SAEs, and AESIs after
	the dose up to Day 31 (i.e. with onset from Day 1 to Day
	30 post vaccination), as classified by the MedDRA SOC
	and PT, will be tabulated by treatment group. The same
	tabulation will be performed for causally related MAAEs,
	SAEs and AESIs during this period (i.e. with onset from
	Day 1 to Day 30 post vaccination).
	The detailed listings of SAEs, AESIs and COVID-19
	cases will also be produced.

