# **Risk Assessment**

Important/potential/risk of clinical significance	Summary of data/rationale for risk	Mitigation strategy
	therapy, to avoid the risk of hematoma following the injection.	Participants with any medical condition that in judgment of the investigator would make intramuscular injection unsafe will be excluded from study enrollment.
mRNA-CR-04 vaccine		
Myocarditis/pericarditis	Myocarditis/pericarditis are considered as an important identified risk for marketed mRNA COVID-19 vaccines [EMA, 2021a; EMA, 2021b; FDA, 2021a; FDA, 2021b] The estimated reporting rates of myocarditis in younger adults [25- to 29-year old] following the first and the second doses of BNT162b2 vaccine were 0.7 and 5.7 per 100 000, respectively and following the first and the second doses of mRNA-1273 vaccine were 1.8 and 11.2 per 100 000, respectively [CDC, 2021]. The same reporting trend was observed following booster mRNA vaccination, except for age, with most cases reported in older adults [ACIP, 2021].	Participants at increased risk of myocarditis/pericarditis or with medical history of myocarditis/pericarditis are excluded from study enrollment. Participants will also be instructed (via informed consent form) to be alert for symptoms of myocarditis/pericarditis and immediately contact the site if any of these symptoms occur. Participants will be tested for cardiac troponin I and undergo EKG at the screening and on D8 after study intervention administration. Participants will receive close medical supervision and medical assessments (e.g., laboratory testing) during the study. Moreover, myocarditis/pericarditis will be collected as an AESI and adjudicated (refer to Section 8.3.8,Section 8.4.4 and Section 10.3.5)

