### 8.2.1. Biological samples

Sample type	Quantity	Unit	Timepoint	Subset name
			Screening (D-7 to D-1)	All screened participants
Nasopharyngeal swab for	NIA		Visit 1 (D1)	
SARS-CoV-2 test	NA	NA	Visit 2 (D8)	All enrolled participants
			Visit 3 (D15)	
Plood for ESH	~25	ml	Sereening (D 1/ to D 1)	Female participants to confirm
	~2.5	∟	Screening (D-14 to D-1)	non-childbearing potential
Blood for Troponin I	~25	ml	Screening (D-14 to D-1)	All screened participants
	°Z.J	111∟	Visit 2 (D8)	All enrolled participants
	~6	mL	Screening (D-14 to D-1)	All screened participants
Blood for hematology/			Visit 1 (D1)	
biochemistry			Visit 2 (D8)	All enrolled participants
			Visit 3 (D15)	
Blood (serum) for vaccine-			Visit 1 (D1)	
induced humoral immune	~15		Visit 3 (D15)	All oprolled participants
response and to assess SARS-	~15	111∟	Visit 4 (D31)	All enfolied participants
CoV2 N protein serology			Visit 5 (M6)	
			Visit 1 (D1)	
Blood (PBMCs) for cellular	~50	mL	Visit 3 (D15)	All oprolled participants
immune response	~50		Visit 4 (D31)	
			Visit 5 (M6)	

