## 8.3.4. EKGs

• 12-lead EKGs will be obtained as outlined in the SoA (see Section 1.3) using an EKG machine that automatically calculates the heart rate and measures PR, QRS, QT, and QTc intervals.

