## 8.3.6. Clinical safety laboratory tests

- See Section 10.2.1 for the list of clinical laboratory tests to be performed in accordance with lab manual and the SoA (Section 1.3).
- The investigator must review the laboratory results, document this review, and record any clinically significant changes occurring during the study as an AE. The laboratory results must be retained with source documents.
- Abnormal laboratory findings associated with the underlying disease are not considered clinically significant unless judged by the investigator to be more severe than expected for the participant's condition.
- All laboratory tests with values considered clinically significantly abnormal during participation in the study or within 31 days after the last dose of study intervention should be repeated until the values return to normal or baseline or are no longer considered clinically significant by the investigator or medical monitor.
  - In the absence of a diagnosis, abnormal laboratory findings assessments or other abnormal results the investigator considers clinically significant will be recorded as an AE or SAE, if they meet the definition of an AE or SAE (refer to Section 10.3.1 and Section 10.3.2).
  - If clinically significant values do not return to normal/baseline within a period of time judged reasonable by the investigator, the etiology should be identified, and the sponsor notified.
  - If laboratory values from non-protocol-specified laboratory tests performed at the institution's local laboratory require a change in participant management or are considered clinically significant by the investigator (e.g., SAE or AE), then the results must be recorded.
- Analyses of safety laboratory samples collected at Day 1 through the EoS will be performed at the central laboratory using the same grading standards.
- Laboratory data will be graded according to the FDA guidance for industry "Toxicity grading scale for healthy adults and adolescent volunteers enrolled in preventive vaccine clinical trials" dated September 2007 [FDA, 2007]. These laboratory values serve as guidelines and are dependent upon laboratory normal parameters. Normal reference ranges should be provided to demonstrate that they are appropriate. Any laboratory parameters not listed in Table 19 and Table 20 (Section 10.2.2) will not be graded and will be assessed on case-by-case basis.

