#### Asymptomatic myocarditis/pericarditis:

At the Day 8 (Visit 2), all participants will be assessed by 12-lead EKG for evidence of asymptomatic myocarditis or pericarditis, based on evidence that rare cases of myocarditis or pericarditis have occurred most frequently within 7 days of vaccination
[CDC, 2023]. All participants will also have a 12-lead EKG examination at screening, to provide a baseline for comparison.

Asymptomatic acute myocarditis/pericarditis is defined as electrocardiographic changes suggestive of acute myocardial injury occurring in an asymptomatic participant within 6 weeks after administration of a COVID-19 mRNA vaccine, if other causes of acute cardiac disease are excluded. If any of the EKG changes suggestive of myocarditis and pericarditis listed above are detected at the surveillance EKG occurring at the Day 8 visit, the findings will be reviewed by the investigator.

If deemed appropriate the participant will be referred to a local cardiologist. If a diagnosis of myocarditis or pericarditis is confirmed, then the participant will be further evaluated and receive cardiology consultation, including cardiac enzyme assessment, echocardiography, or other assessments deemed clinically warranted by the treating clinician.

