# 10.2. Appendix 2: Clinical laboratory tests

### 10.2.1. Protocol required safety laboratory assessments

The tests detailed in Table 18 will be performed by the CRO PPD.

Table 18 P	rotocol required safety laboratory assessments

Laboratory	Parameters			
assessments				
Hematology	Platelet Count	RBC Indices:		WBC count with
	RBC Count	MCV		differential:
	Hemoglobin	MCH		Neutrophils
	Prothrombin Time /	%Reticulocytes		Lymphocytes
	INR			Monocytes
				Eosinophils
				Basophils
Clinical chemistry	BUN		AST	Total and direct bilirubin
	Creatinine		ALT	
			ALP	
Other tests	Follicle stimulating hormone (as needed in WONCBP only)			
	Cardiac troponin (troponin I)			
	
 
[Serum or urine hCG pregnancy test (as needed for WOCBP)]
 
			
	The results of each test carried out locally must be entered in the eCRF.			eCRF.

NOTES:

All events of ALT  $\ge$  3x ULN AND total bilirubin  $\ge$  2x ULN (>35% direct bilirubin) or INR >1.5, which may indicate severe liver injury (possible Hy's Law), must be reported as an SAE.

All events of Troponin I  $\ge$  2 x baseline value, may require clinical review.

Local urine testing will be standard for the protocol unless serum testing is required by local regulation or IRB/IEC.

ALP: Alkaline phosphatase; ALT: Alanine aminotransferase; AST: Aspartate aminotransferase; BUN: Blood urea nitrogen; eCRF: electronic Case report form; hCG: human Chorionic gonadotropin; INR: International normalized ratio; IEC: Independent ethics committee; IRB: Institutional review board; MCH: Mean corpuscular hemoglobin; MCV: Mean corpuscular volume; RBC: Red blood cell; SAE: Serious adverse event; ULN: upper limit of normal; WBC: White blood cell; WONCBP: Woman of non-child-bearing potential; WOCBP: Woman of childbearing potential.

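### The SAP plans no by-group summary of the Day 8 EKG findings and does not clearly place troponin I in its laboratory tables

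*SAP*

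**What the plan says.** Protocol 2.3 gives the mitigation for myocarditis/pericarditis: "Participants will be tested for cardiac troponin I and undergo EKG at the screening and on D8 after study intervention administration". Protocol 8.4.4.2.1 gives the purpose of the Day 8 tracing: "all participants will be assessed by 12-lead EKG for evidence of asymptomatic myocarditis or pericarditis", with the screening EKG as the comparator. Under Protocol 8.3.4 the tracings are taken "using an EKG machine that automatically calculates the heart rate and measures PR, QRS, QT, and QTc intervals". Under Protocol 8.3.8 an external cardiologist, blinded to treatment, reads all surveillance EKGs, and those with suggestive changes go to adjudication.

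SAP 4.2.1.1 defines the laboratory output "For each treatment group and for each Hematology and biochemistry parameter". That output consists of normal-range counts with exact 95% CIs by time point, grade increases at Day 8 and Day 15, maximum post-dose grade against baseline, and a listing of safety laboratory results. The word troponin does not occur in the SAP. EKG occurs only in its list of abbreviations.

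The protocol keeps troponin apart from haematology and biochemistry. It has its own row in the Schedule of Activities, its own sample row ("Blood for Troponin I", Protocol 8.2.1), and sits under other tests in Table 18. Troponin is not in the grading tables, and Protocol 8.3.6 states: "Any laboratory parameters not listed in Table 19 and Table 20 (Section 10.2.2) will not be graded and will be assessed on case-by-case basis".

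**The concern.** Every participant is measured before and after dosing for the one organ-specific risk that the protocol singles out for surveillance, yet no planned table compares those measurements across doses. The planned cardiac outputs count events. A laboratory or EKG change becomes an AE only if the investigator judges it clinically significant (Protocol 8.3.6 and 10.3.1). A Day 8 EKG change leads to a cardiology referral only if that is thought appropriate (Protocol 8.4.4.2.1).

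Each of these decisions is made one participant at a time. A modest upward drift in troponin at the top dose, or a scatter of minor EKG changes that are each unremarkable, could pass all of them and still differ from placebo. The trial exists to inform the choice of dose, so this is the comparison a reader of the report would want.

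**Working it through.** **1. Which planned outputs can carry each measurement**

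- *Grade tables (SAP 4.2.1.1).* Troponin is in neither Protocol Tables 19–20 nor SAP Tables 6–7, so it cannot enter. EKG is not a laboratory parameter.
- *Normal-range counts (SAP 4.2.1.1).* These include troponin only if the programmer treats it as biochemistry, which Table 18 does not. Even then they show no change from baseline, so a shift inside the normal range is invisible. EKG is not covered.
- *Laboratory listing (SAP 4.2.1.1).* It may carry troponin, because Table 18 lists the required safety laboratory tests. EKG is not covered.
- *AE and AESI tables (SAP 4.2.1.1, 4.2.1.3, 4.3.1.1, 6.2.3.11).* These are by treatment group, but hold only what has been recorded as an AE or identified as an AESI.
- *Day 15 report (SAP 4.8.1).* By treatment group, without individual listings, so the listing route is closed there.
- *Protocol 9.4.1.* It plans no EKG or troponin summary either.

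**2. How many measurements are affected**

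Planned enrolment is 72 + 42 = 114. With full attendance there is one post-dose EKG and one post-dose troponin each at Day 8, so 114 of each. Planned vaccinees number 5 × 18 = 90 and placebo recipients 18 + 6 = 24.

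**3. The plan's own detection figures**

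SAP 5 states 60.3% and 85% for at least one affected participant among 18. With P = 1 − (1 − p)^18:

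- p = 0.05: 1 − 0.95^18 = 0.603
- p = 0.10: 1 − 0.90^18 = 0.850

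Both reproduce. At p = 0.01 and 0.02 the probabilities are 0.165 and 0.305.

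**4. What diagnosed cases alone could show**

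The highest reporting rate cited in Protocol 2.3 is 11.2 per 100,000. Purely as an illustration, 90 × 11.2/100,000 = 0.01 expected cases. That rate is for 25- to 29-year-olds after a second dose of a marketed vaccine. It is not a rate for this product, nor one under EKG surveillance.

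**5. Precision of the missing tables**

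The exact 95% upper limit for 0/n is 1 − 0.025^(1/n):

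- n = 18 (3, 30 or 100 µg): 18.5%
- n = 24 (pooled placebo, Parts A and B): 14.2%
- n = 36 (10 µg, Parts A and B): 9.7%

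For one and two abnormal results among 18, the exact intervals are 0.1–27.3% and 1.4–34.7%.

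For the mean log10 Day 8/baseline troponin ratio at n = 18, the 95% half-width is t(0.975, 17)/√18 = 0.497 SD. The documents give no troponin SD. Assuming 0.1, 0.2, 0.3 or 0.45 on the log10 scale, the half-width is a factor of 1.12, 1.26, 1.41 or 1.67.

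**6. The troponin criterion is stated in two ways**

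Protocol 8.4.4.2.1 lists, among its EKG changes, a troponin I value above 2 ULN of baseline that is confirmed on repeat testing. The note to Table 18 refers to values of at least twice baseline. These are different conditions, so a count of participants meeting the criterion is not defined until the two are reconciled.

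**The case against.** The event route is wider than it may seem. All surveillance EKGs get a blinded expert read, suggestive ones are adjudicated, and the protocol's definition of asymptomatic myocarditis/pericarditis rests on EKG changes, so a subclinical case can become an AESI. SAP 6.2.3.11 also draws in AEs under several broad cardiac queries. The iSRC reviews all sentinel safety data at Day 8, including laboratory data, and the SRT is unblinded after the Part A Day 15 analysis. EKG and troponin are mitigation measures, not listed endpoints, and the SAP follows the protocol in not tabulating them. At 18 per group the tables would be imprecise.

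All of that stands, and it rules out three stronger readings that a reader might infer:

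- *The cardiac data would go unreported.* The documents do not support this. Recorded AEs and AESIs are tabulated by group, and troponin may be in the final listing.
- *Troponin is excluded from the laboratory tables.* This is not settled. The SAP does not define a biochemistry parameter, and the other-tests row, which also holds FSH and hCG, may be only a layout category. The fault is ambiguity.
- *Day 8 EKG and troponin are the only cardiac information on dose.* AEs, adjudicated cases and unblinded safety review also contribute.

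What the objection does not remove is the absence of any by-group EKG output and of any planned change-from-baseline summary for troponin. Committee review protects participants but is not an output of the study report. Imprecision is no reason to omit a table in a wholly descriptive study that gives routine laboratory parameters exact intervals at the same group sizes.

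**Conclusion.** The point holds as a gap in by-dose summarising. Changes below the AE and AESI thresholds would not be compared across doses. For EKG this is certain from the text. For troponin it depends on how biochemistry is read, and even on the generous reading a shift within the normal range would be missed, in the Day 15 report as well as the final one.

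The size is about 114 Day 8 results of each kind. The 60.3% and 85.0% figures are chances of seeing at least one affected participant among 18, assuming true rates of 5% and 10%; they are not chances of separating a dose from placebo. No stated figure in the plan is wrong and no planned analysis is invalid. This is a cheap improvement.

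**What to change.** Add to SAP 4.2.1.1, on the Exposed Set, by treatment group with pooled placebo, for Part A, Part B and combined:

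- **Troponin I** at baseline (screening) and Day 8: n (%) within and above the normal range with exact 95% CI, a shift table, and the distribution of individual Day 8/baseline ratios. State how values below the assay limit are handled; SAP 6.2.3.5 gives no limit for troponin.
- **EKG**: n (%) with an abnormality new at Day 8 versus screening, from the blinded cardiologist's read and at whatever level of detail that read captures, plus change in PR, QRS, QT and QTc. The documents do not show that the read is recorded by category, so confirm this before fixing the table shells.

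Put the by-group tables in the interim and final reports. Keep any participant listing for the final report, since SAP 4.8.1 excludes individual listings at Day 15.

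The sponsor should reconcile the troponin criteria in Protocol 8.4.4.2.1 and Table 18 before tabulating against either. The normal-range counts and ratios do not depend on that choice.

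The cost is SAP wording and a few descriptive tables from measurements already scheduled. No visit, sample or sample size changes. The estimates will be imprecise and some non-specific EKG changes will be displayed; the placebo column gives them context.
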